### **3.2.6 Summaries of Baseline Characteristics, Demographics, and Other Analyses**

#### **Demographic and Baseline Characteristics**

The number and percentage of subjects screened, randomized, the primary reasons for screening failure, and the primary reason for discontinuation will be displayed.

Demographic variables (including age, gender, race, weight, height, and body mass index), baseline characteristics (including baseline asthma status, inhaled corticosteroid use, duration of allergic rhinitis, sensitization type, ragweed specific IgE, wheal size from skin prick test, and number of puffs of bronchodilator used for FEV1 reversibility), primary and secondary diagnoses, and prior and concomitant therapies will be summarized by treatment either by descriptive statistics or categorical tables. The comparability of the treatment groups for each relevant characteristic will be assessed by the summary tables. No statistical hypothesis tests will be performed on these characteristics.

#### **Skin Prick Test (SPT) Analysis**

Descriptive statistics (mean, standard deviation, etc.) of the wheal size determined from the SPT will be provided for all randomized subjects.

### 3.2.7 Multiplicity

A fixed sequence procedure will be applied to control multiplicity. The primary and key secondary efficacy endpoints will be tested in the following order:

- Average TCS during the peak RS;
- Average TCS during the entire RS;
- Average rhinoconjunctivitis DSS during the peak RS;
- Average rhinoconjunctivitis DMS during the peak RS.

A lower order endpoint will be tested only if all higher order endpoints have been tested and claimed statistically significant.

### 3.2.8 Sample Size and Power Calculations

A total of approximately 1000 subjects will be randomized in a 1:1 ratio to either MK - 3641 or placebo. Assuming a 15% dropout rate, this gives approximately 425 evaluable subjects per treatment group.

With 425 subjects per arm, the study will have:

- approximately 90% power (2-sided,  $\alpha = 0.05$ ) to have the upper bound of the 95% CI for relative difference below -10%, and
- more than 90% power (2-sided,  $\alpha = 0.05$ ) to have an estimated relative difference below -15%.

The calculations are based on the assumptions that the true difference between treatment arms in average TCS during peak RS is -2.12, that the average TCS during peak RS from the placebo group is 8.9, and that the standard deviation is 5.60. These assumptions, as well as the assumption on dropout rate, are based on the two MK-3641 (AIT ragweed) adult studies, P05233 and P05234, and the pediatric trial P05239 for MK-7243 (AIT grass).

### 3.2.9 Subgroup Analyses and Effect of Baseline Factors

Analysis for the primary efficacy endpoint will be provided for the following subgroups of baseline factors:

- Baseline asthma status (yes, no);
- Age group (5 to 11 years, 12 to 17 years);
- Gender (male, female);
- Race (Caucasians, non-Caucasians);

- ICS use for subjects with asthma (yes, no);
- Allergen sensitization type (ragweed only, ragweed + others);
- Geographic region (e.g., US, Canada, Europe). Region classification for each study site will be determined before database lock.

In addition, subgroup analysis on the primary efficacy endpoint will be provided for:

- Pollen counts (low, high): The subgroups will be defined based on the median of the subject level accumulated pollen counts during the first 21 days of the pollen season;
- Local application site reaction (had local application site reactions, did not have local application site reactions).

The same ANOVA model as in the primary efficacy analysis will be applied for the subgroup analyses.

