4.0 BACKGROUND & RATIONALE

4.1 Background

Allergic rhinitis/rhinoconjunctivitis (AR/ARC) affects between 10% to 30% of adults and up to 40% of children in the US [1]. Ragweed pollen is one of the most common inhalant allergens in North America, and for many patients ragweed pollen is a cause of their rhinoconjunctivitis symptoms [2]. Until recently, ragweed was predominantly a problem in North America, however, higher rates of ragweed allergy prevalence and sensitization are now seen in some European countries [3].

Allergen-specific immunotherapy consists of administering allergens to an allergic patient in order to induce immunological tolerance to the natural allergen. Subcutaneous immunotherapy (SCIT) has been the main approach for the application of this type of therapy [4]. However, these treatments are associated with risk of severe systemic reactions and must be administered by trained health care personnel at the physician's office. The administration of an oral allergen formulation, such as sublingual immunotherapy tablets, also reduces immediate reactivity to specific IgE antibody and is associated with a favorable safety profile that, in contrast to SCIT, permits self-administration by the patient after the first dose has been shown to be tolerable under physician observation. The predominant adverse reactions when administering allergen sublingually include local allergic events such as oral pruritus, itching of the throat, or swelling under the tongue, which will generally resolve with continuous treatment over the following weeks.

MK-3641 (RAGWITEK^{®3}) is a sublingual immunotherapy (SLIT) tablet approved for use in the United States (US) and Canada for the treatment of short ragweed pollen-induced allergic rhinitis, with or without conjunctivitis, in adults 18 through 65 years of age. It is self-administered at home after the first dose is administered under supervision by a health care professional. To date, MK-3641 has not been studied in children. However, a similar tablet formulation containing Timothy grass (MK-7243) has been shown to be efficacious and safe for children down to 5 years of age. MK-7243 is approved in North America and Europe under the trade names of GRASTEK^{®4} and GRAZAX^{®5}, respectively, for the treatment of allergic rhinitis and conjunctivitis in patients 5 to 65 years of age.

Refer to the Investigator's Brochure (IB)/approved labeling for detailed background information on MK-3641.

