4.1.1 Pharmaceutical and Therapeutic Background

MK-3641 is a freeze-dried, rapidly (within seconds) dissolving SLIT tablet containing *Ambrosia artemisiifolia* (short ragweed) extract, specifically 12 Amb a 1-U of the major short ragweed allergen Amb a 1. The effect of MK-3641 on alleviating the symptoms of ragweed pollen-induced allergic rhinoconjunctivitis is thought to be mediated via immunization of oral Langerhans cells inducing immunologic responses within the oral mucosa or local lymph nodes after sublingual allergen exposure and potential uptake into local tissues [5].

The placebo tablet is indistinguishable from the active tablet in appearance but contains no ragweed allergen.

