5.2.2 Timing of Dose Administration

The first dose of study drug will be administered under supervision at the study site at Visit 2. Subsequent dosing will be performed once daily at home by the subject/parent/guardian at approximately the same time each day for up to approximately 28 weeks and should occur at a time of the day that would allow the parent/guardian to keep the subject under observation for AEs for approximately 30 minutes after administration.

5.2.2.1 In-Clinic Dosing at Visit 2

At Visit 2, the first dose of study drug will be administered under supervision at the study site, and then the subject will be required to stay at the study site for an observation period of approximately 30 minutes to assess any AEs. Prior to administration of the first dose of study drug, the investigator should discuss well-known immediate application site reactions and severe AEs requiring medical evaluation and/or the use of rescue emergency medications (such as antihistamines, epinephrine, etc.) with the subject/parent/guardian. The site should record the duration of AEs (in minutes) following the first administration of the study drug at the randomization visit. If any significant AE such as wheezing, dyspnea, severe oral swelling, or signs of generalized anaphylactic reaction is observed or reported, the investigator or medically qualified sub-investigator must evaluate the subject to determine whether treatment of the adverse reaction should be initiated. In such cases, the observation period should be extended for at least an additional 30 minutes. When the subject/parent/guardian leave the study site, instructions should be given to contact the study site immediately if the reaction reoccurs or a new reaction appears. If the investigator determines that a subject cannot leave the study site but needs further attention not otherwise

available at the study site, the subject will be transferred to an appropriate facility such as an emergency room.

Subjects not experiencing clinically significant reactions may leave the study site approximately 30 minutes after the first dose of study drug has been given. The subject/parent/guardian should be instructed to contact the study site immediately if any reaction occurs after leaving the study site.

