8.2.8 Subgroup Analyses and Effect of Baseline Factors

Analysis for the primary efficacy endpoint will be provided for the following subgroups of baseline factors:

- Baseline asthma status (yes, no);
- Age group (5 to 11 years, 12 to 17 years);
- Gender (male, female);
- Race (Caucasians, non-Caucasians);
- ICS use for subjects with asthma (yes, no);
- Allergen sensitization type (ragweed only, ragweed + others);
- Geographic region (e.g., US, Canada, Europe). Region classification for each study site will be determined before database lock.

In addition, subgroup analysis on the primary efficacy endpoint will be provided for:

- Pollen counts (low, high): The subgroups will be defined based on the median of the subject level accumulated pollen counts during the first 21 days of the pollen season;
- Local application site reaction (had local application site reactions, did not have local application site reactions).

The same ANOVA model as in the primary efficacy analysis will be applied for the subgroup analyses.

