### **3.2.3.2 Safety Endpoints**

#### **Tier 1 Safety Endpoints**

- Proportion of subjects reporting pre-specified local application site reactions (including adverse events related to lip swelling/edema, mouth swelling/edema, palatal swelling/edema, swollen tongue/edema, oropharyngeal swelling/edema, pharyngeal edema/throat tightness, oral pruritus, throat irritation, tongue pruritus, and ear pruritus);
- Proportion of subjects reporting anaphylaxis and/or systemic allergic reactions;
- Proportion of subjects treated with epinephrine.

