##### **3.2.5.1 Statistical Methods for Efficacy/Immunologic Analyses**

###### **Primary Efficacy Analysis**

The primary efficacy endpoint for the current trial is the average TCS during the peak ragweed season. It will be analyzed using the ANOVA model, which includes fixed effects of treatment, baseline asthma status (yes, no), age group (5 to 11 years, 12 to 17 years), pollen season, and pollen region nested within pollen season. Pollen region will be defined based on pollen station and may include several sites within an acceptable distance between the pollen counters and corresponding sites.

Two-sided 95% CI of the treatment difference in adjusted means will be presented. Also, the treatment difference in adjusted means relative to the adjusted mean of the placebo group will be presented as a percentage with corresponding 2-sided 95% CI derived using the bootstrap method. No missing data will be imputed.

The normality assumption of the ANOVA model will be checked using the Shapiro-Wilk test and inspection of the Q-Q plot. If a severe violation is observed, the primary analysis will be based on Wilcoxon Rank Sum test; the p-value will be reported together with the associated Hodges-Lehmann estimate of the treatment difference and its 2-sided 95% CI. Also, the difference in the treatment group medians relative to the median of the placebo group will be presented as a percentage with the corresponding 2-sided 95% CI derived using the bootstrap method.

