### 3.2.5.2 Statistical Methods for Safety Analyses

Safety and tolerability will be assessed by clinical review of all relevant parameters including adverse experiences (AEs), laboratory tests, and vital sign measurements.

The analysis of safety results will follow a tiered approach [Table 4]. The tiers differ with respect to the analyses that will be performed. Tier 1 safety endpoints will be subject to inferential testing for statistical significance with p-values and 95% CIs provided for between- group comparisons. Tier 2 safety endpoints will be evaluated via point estimates and 95% CIs for between-group comparisons. Tier 3 safety endpoints will be evaluated via point estimates only.

For this trial, Tier 1 safety endpoints include:

- Proportion of subjects reporting pre-specified local application site reactions (including adverse events related to lip swelling/edema, mouth swelling/edema, palatal swelling/edema, swollen tongue/edema, oropharyngeal swelling/edema, pharyngeal edema/throat tightness, oral pruritus, throat irritation, tongue pruritus, and ear pruritus);
- Proportion of subjects reporting anaphylaxis and/or systemic allergic reactions;
- Proportion of subjects treated with epinephrine.

For the analysis of “Proportion of subjects treated with epinephrine”, the denominator will include all subjects in the ASaT population, regardless of whether self-injectable epinephrine was provided or not. Meanwhile, a sensitivity analysis will be conducted where the denominator will include subjects in the ASaT population who were provided with self-injectable epinephrine, and the numerator will be subjects from the denominator subjects who were treated with epinephrine.

Tier 2 safety endpoints for this trial include:

- Proportion of subjects with any AE;
- Proportion of subjects with any serious AE;
- Proportion of subjects with any drug-related AE;
- Proportion of subjects with any serious and drug-related AE;
- Proportion of subjects who discontinue due to an AE;
- Proportion of subjects with specific AEs or SOCs (incidence  $\geq$  1% subjects in one or more of the treatment groups).

The Tier 1 and Tier 2 safety endpoints will be analyzed using the stratified Miettinen and Nurminen method [1985] with baseline asthma status and age group as stratification

factors.

Tier 3 safety endpoints for this trial include:

- Change from baseline in laboratory test parameters at each post-baseline visit;

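### The local-reaction subgroup compares active with placebo within groups formed after dosing, so neither contrast is a randomised comparison

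*SAP*

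**What the plan says.** Protocol 8.2.8 and sSAP 3.2.9 list subgroup analyses of the primary endpoint for baseline factors such as asthma status, age group and sex. A second list follows, with pollen count and "Local application site reaction (had local application site reactions, did not have local application site reactions". One rule covers both lists: "The same ANOVA model as in the primary efficacy analysis will be applied for the subgroup analyses". That model is the one "which includes fixed effects of treatment, baseline asthma status (yes, no), age group (5 to 11 years, 12 to 17 years", together with pollen season and pollen region within season. Its treatment term is thus estimated once among children who reacted and once among those who did not.

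Other sections describe what kind of variable this is:

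- Protocol 4.1: "The predominant adverse reactions when administering allergen sublingually include local allergic events such as oral pruritus".
- Protocol 4.1.1: "The placebo tablet is indistinguishable from the active tablet in appearance but contains no ragweed allergen".
- Protocol 5.2.2.1, on what must happen before the first dose: "the investigator should discuss well-known immediate application site reactions".
- Protocol 7.1.2.8: the duration of the pre-specified local events is recorded at the first supervised dose.
- sSAP 3.2.3.2, Tier 1: "Proportion of subjects reporting pre-specified local application site reactions".
- sSAP 3.2.5.2: "Tier 1 safety endpoints will be subject to inferential testing for statistical significance".

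Neither document adds a caveat to the reaction subgroup, calls it descriptive only, or gives a causal method for it. Neither subgroup section gives a term list or time window for the reaction.

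**The concern.** A subgroup contrast keeps the protection of randomisation when the subgroup is fixed before treatment or cannot be changed by it. Reaction status is neither. It arises after dosing, the plan expects the active tablet to cause it, and the safety analysis tests it between arms as an outcome of treatment.

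Active-arm reactors include children who reacted because of the allergen; placebo-arm reactors reacted without it. These may be different kinds of children, with different TCS whatever the tablet does. The two sets of non-reactors can differ in the same way. Adjustment for asthma, age group, season and region does not make them comparable on the unmeasured tendency to react.

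At stake is how a pre-specified table is read. Two modelled treatment effects side by side invite the conclusion that reactors benefit more, or less, than non-reactors. The table cannot show that, because its two estimates can differ from each other and from the truth even when every child benefits equally.

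**Working it through.** **The plan's own figures.** The plan gives no figure for this subgroup. Its sample-size inputs (Protocol 8.2.7, sSAP 3.2.8) are a true difference of -2.12, a placebo mean of 8.9, an SD of 5.60 and 500 x (1 - 0.15) = 425 evaluable per arm. They reproduce its power statement. With the placebo mean treated as fixed, the distance from the -10% bound is 2.12 - 0.10 x 8.9 = 1.23. The standard error is 5.60 x sqrt(2/425) = 0.384. Then 1.23/0.384 - 1.96 = 1.24, which gives 89.3% power against about 90% stated. The effect and SD are used below.

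**Assumptions not in the documents.** Reaction rates of 50% on active and 15% on placebo; a correlation rho between reaction tendency and TCS; the same true effect, -2.12, in every child; no covariate adjustment.

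**Model.** Let L be a standard normal tendency to react. A child reacts when L exceeds the threshold z that gives the arm's rate p. Then

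- mean of L in reactors = phi(z)/p
- mean of L in non-reactors = -phi(z)/(1 - p)

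At p = 0.50 these are +0.798 and -0.798. At p = 0.15 they are +1.554 and -0.274.

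Expected contrast within a reaction stratum = -2.12 + 5.6 x (rho_active x mean L on active - rho_placebo x mean L on placebo).

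**Example, rho = +0.2 in both arms.**

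- Reactors: -2.12 + 5.6 x 0.2 x (0.798 - 1.554) = -2.97
- Non-reactors: -2.12 + 5.6 x 0.2 x (-0.798 + 0.274) = -2.71

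| rho active | rho placebo | Reactors | Non-reactors |
|---|---|---|---|
| 0 | 0 | -2.12 | -2.12 |
| +0.2 | +0.2 | -2.97 | -2.71 |
| -0.2 | -0.2 | -1.27 | -1.53 |
| +0.2 | 0 | -1.23 | -3.01 |
| 0 | +0.2 | -3.86 | -1.81 |

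In the second row both subgroup estimates exceed the overall effect, although no child has an effect other than -2.12. In the last two rows they move apart and suggest an interaction that does not exist. A simulation with 2,000,000 per arm agreed with the four biased rows to within 0.02 and kept the overall effect between -2.11 and -2.13. It draws from the same model, so it checks the arithmetic only.

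**Other assumed rates, equal rho in both arms.** At 50% against 20% and rho = 0.2, the contrasts are -2.79 and -2.62. With 425 per arm the strata hold about 212 against 85 reactors and 212 against 340 non-reactors, so 1:1 balance is lost. If treatment had no effect at all, a nominal 5% test would then reject 15.5% of the time in reactors and 17.6% in non-reactors. Across the rate pairs tried (30-70% active, 10-30% placebo, |rho| up to 0.3), the bias ran from zero to about 1.6 TCS points, the largest at 50% against 10%. It was zero throughout when both arms reacted at 20%.

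**The case against.** The strongest objection concerns importance. The table is outside the fixed sequence, no decision in either document depends on it, and the plan keeps it in a list separate from the baseline factors without claiming a causal reading or an interaction test. It might be meant as a check on unblinding, since the tablets are matched in appearance and reactions could reveal allocation. All of this bears on severity, and it limits the point to a supportive table. It does not make the contrasts valid: the same model is applied to both lists, no unblinding purpose is stated, and such a check would still mix selection with any effect of unblinding.

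The numbers are also open to challenge. The rates and correlations are assumed, and the most striking rows need a correlation in one arm only, for which there is no evidence. With equal correlations of size 0.2 at 50% against 15%, the shifts are 0.59 to 0.85. The planned model adjusts for covariates, so the relevant residual correlation may be smaller. This stands, and the table above is an illustration, not an estimate or a bound.

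Finally, a descriptive display lets a reader subtract the same two means, so a warning label on the existing table might do. That is partly right, since the label does much of the work. But keeping adjusted effects with confidence intervals under a label still presents them as treatment effects.

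**Conclusion.** The concern holds. As written, the plan produces two active-versus-placebo estimates that randomisation does not protect, without a caveat.

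This rests on the reaction being a post-dose event that the allergen is expected to cause, which the protocol supports. It also rests on reading the undefined subgroup term as the same kind of event as the Tier 1 local reactions. The structural problem remains under any post-dose definition on which the tablet affects the reaction.

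The sign and size of the bias cannot be fixed from the documents. Under the model used here there is none if reaction tendency is unrelated to TCS in both arms, or if the arms share both the reaction rate and the correlation. An allergen-free placebo makes equal rates unlikely. The harm is confined to interpreting this one table.

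**What to change.** In sSAP 3.2.9, take local application site reaction out of the subgroups to which the primary ANOVA is applied, and state that this replaces the corresponding item in Protocol 8.2.8. Protocol 8.2 provides for non-confirmatory changes made before final database lock to be documented in the sSAP.

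In its place:

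- Define the event: the term list (for example, the Tier 1 list, if that is what is meant) and the time window.
- Tabulate, by arm and reaction status, the number of children and descriptive statistics for average TCS in the peak season.
- Label the table as a non-randomised, non-causal comparison, with no model-based treatment effect, confidence interval for a difference, or p-value.

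The cost is a few lines of sSAP text, minor programming and the loss of one supportive table in its present form. The sample size, data collection, primary analysis and testing sequence do not change.

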### 3.2.10 Interim Analyses

No efficacy interim analysis is planned for this trial. Safety data will be reviewed by an eDMC.

### 3.2.11 Compliance (Medication Adherence)

For each subject, percent compliance will be calculated using the following formula:

$$\text{Percent Compliance} = \frac{\text{Number of Days on Therapy}}{\text{Number of Days Should Be on Therapy}} \times 100\%$$

A day within the study will be considered an “On-Therapy” day if the subject takes all required medication as instructed in Section 5.2 of the protocol. When a subject takes less than or more than the required medication on a day, that day is not considered an On-Therapy day.

For subjects who are followed for the entire study period, the “Number of Days Should be on Therapy” is the number of days from the first scheduled treatment day to the last scheduled treatment day. For subjects who discontinue from the study, the “Number of Days Should Be on Therapy” is the number of days from the first scheduled treatment day to the last dose day.

Summary statistics will be provided on percent compliance for the ASaT population.

